AIM 4: Perform an economic evaluation alongside this randomized controlled trial to estimate the cost effectiveness of the two interventions compared to each other and usual care, for uptake of CGRA services from the societal and payer perspectives. This aim provides information about the value of the interventions from both societal and payer perspectives, given a cost per effect measure and the uncertainty surrounding the estimate.

[figure not shown]
B. Hypotheses / Research Question(s)

Primary Hypothesis: Compared to UC, CGRA (genetic counseling) uptake at 6 months (primary outcome) will be highest among women participating in the TCN arm followed by women participating in the TP arm.

1.2 Research Significance (Briefly describe the following in 500 words or less):

HBOC Cancer Risks and Genetic Risk Prediction. Identification of individuals at increased risk of HBOC is crucial for cancer survivors and their families to benefit from biomedical advances. In 2015, approximately 254,000 new cases of ovarian cancer and female breast cancer were diagnosed in the U.S. Germline mutations in the BRCA1 and BRCA2 genes account for 5-10% of breast cancers and 15% of ovarian cancers.¹⁻³ This translates to 14,000-27,000 high-risk cancer survivors who may be impacted by HBOC. Women with inherited HBOC gene mutations who have had breast cancer are at higher risk of ovarian cancer and a second breast cancer (Figure 1), and possibly other cancers.⁴

Technological advances in DNA sequencing have now made it possible to test multiple genes simultaneously using multiplex gene panels.^{2,5-18}

[figure not shown]

CGRA Personalizes Care and is Recommended for

High-Risk Breast and Ovarian Cancer Survivors. CGRA is an evidence-based strategy that informs medical management options that can improve outcomes.^{14,17,19} CGRA involves genetic counseling +/- genetic testing. There is evidence that CGRA by genetic professionals improves accuracy of risk perceptions, enables informed decision making, personalizes care, and does not cause adverse psychological outcomes.^{14,16,20-22} National

organizations have issued guidelines recommending CGRA for breast and ovarian cancer survivors who may be at risk for HBOC.^{17,20,23,24} CGRA in HBOC survivors impacts public health (Figure 2).^{4,17} If a mutation is identified, testing for the known gene mutation can be offered to relatives to determine if they have the cancer predisposition.^{20,25}

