
Economic Analysis: **Aim 4** will measure the incremental cost of implementing the interventions from a payer and societal perspective. The payer in this case would be the entity responsible for funding the cancer registry considering patient ascertainment and intervention implementation; therefore, we will estimate recruitment costs, intervention development and delivery costs and downstream costs up to 1-year post intervention. The societal perspective in theory includes all goods and services consumed as a result of the intervention, including the payer costs and patient costs: deductibles, copayments, and cost-sharing for direct medical goods and services in addition to direct non-medical goods and services such as transportation to appointments, and indirect, or opportunity costs incurred as part of the intervention.¹⁸⁹ We will use micro-costing techniques as recommended by the US Panel on Cost-Effectiveness in Health and Medicine¹⁹⁰ and utilized in our past research on the costs of behavioral interventions.^{54,178,179} Implementation costs will include labor (e.g., registry and study staff, MI trainer, health education specialists) and non-labor (e.g., printing, mailing, costs of CGRA and genetic tests, telephone

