charges, patient-related travel time). Costs will be grouped as variable and fixed costs. We focus on costs of replicating delivery of the intervention and the immediate down-stream consequences (e.g., obtaining CGRA and genetic testing). Costs will be estimated via direct elicitation from participants and medical records to assign fixed price weights. We consider the following outcomes based on *a priori* trial specifications: 1) average cost per patient for ascertainment, scheduling, health education specialist-participant interaction time; 2) average cost per CGRA and genetic testing; and 3) average time spent with health education specialist. We will also examine overall health care use (including, visits to genetic professionals and other providers, and genetic testing) by study arm (and covariates as needed) at 6 months and 12 months. The incremental cost-effectiveness of one method over another is derived from using the following formula: $Incremental\ cost-effectiveness\ A = (C_A - C_B)/(E_A - E_B)$ where C_A and C_B refer to average total costs of each alternative and E_A and E_B refer to average total effectiveness for each alternative. The resulting incremental cost effectiveness ratio (ICER) calculated for each combination of comparators, TCN, TP, and UC, can be used to assess the value provided by alternative A when compared to alternative B, as it represents the investment required for each additional unit of effect gained. All analyses of cost and effectiveness will be completed on an intent-to-treat basis. Uncertainty in estimates will be tested using probabilistic modeling and sensitivity analysis to assess key drivers of results such as rural/urban residence, cancer type, ethnicity, language preference, age, education, household income and family composition (have at least one living at risk first-degree relative).¹⁹¹ Uncertainty in the ICER will be evaluated using cost-effectiveness acceptability curve plots.¹⁹²

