An intent-to-treat principle was followed in the analysis. Demographic and clinical characteristics of participants were compared across the 3 arms using ANOVA and χ^2 analysis. Logistic regression analysis was employed to compare the medically verified CGRA uptake (yes/ no) at 12months between TCN vs UC and TP; a binary intervention variable (TCN vs TP; TCN vs UC) was added to logistic models separately. Negative outcome imputation and multiple imputation were then used as sensitivity analyses to determine whether the intervention effect estimates were sensitive to imputation and if the conclusions were consistent. Negative outcome imputation assumed that CGRA did not occur if there was no documented verification. Multiple imputation was based on verified CGRA within 12months and demographic and clinical variables. Twenty-five imputed datasets were used to provide a combined estimate for missing values based on Rubin's rule, using Proc MI and Proc MIANALYZE in SAS v9.4. To estimate the cumulative probability of medically verified CGRA uptake following the intervention to 12-month follow-up, Kaplan-Meier estimates were calculated along with the 95% confidence intervals for each study arm. Participants were censored if they were lost to follow-up, or the event did not occur within the 12- month follow-up. All tests of statistical significance were 2-sided.

Analysis includes costs that would be incurred while implementing this intervention in a clinical practice for 212 patients (the number of patients in the TCN arm). Costs of intervention development and study-specific costs were excluded; we excluded costs of participant ascertainment and recruitment, participants' compensation, and survey administration.

The costs include the following sources: (1) training health coaches, (2) brochure printing and mailing, (3) staff costs consisting of salaries and overhead for administrative staff and health coaches, (4) participant time, and (5) downstream genetic counseling and testing and related costs. Costs were calculated in 2022 dollars from a societal perspective.

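### Aim 4 promises a payer as well as a societal economic evaluation, but the SAP specifies only a societal, clinic-based one and drops the planned ascertainment cost without explanation

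*SAP*

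**What the plan says.** **Protocol.** Section 1.1, under Aim 4, states: "This aim provides information about the value of the interventions from both societal and payer perspectives". Section 1.6.B repeats both perspectives under Secondary Objective 3. Section 6.1.A (Economic Analysis) says that Aim 4 "will measure the incremental cost of implementing the interventions from a payer and societal perspective" and then says who the payer is: "The payer in this case would be the entity responsible for funding the cancer registry considering patient ascertainment and intervention implementation". As a consequence of that definition it commits that "we will estimate recruitment costs, intervention development and delivery costs and downstream costs up to 1-year post intervention". The same section names, among its a priori economic outcomes, "average cost per patient for ascertainment, scheduling, health education specialist-participant interaction time". It also plans an ICER for each pairing of TCN, TP and UC, and says the societal perspective contains the payer costs.

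**SAP.** Item 5 gives a single perspective: "Costs were calculated in 2022 dollars from a societal perspective". The setting is a clinical practice treating 212 patients, the size of the TCN arm. On scope it says "Costs of intervention development and study-specific costs were excluded" and "we excluded costs of participant ascertainment and recruitment". The costs it keeps are coach training, brochure printing and mailing, staff costs, participant time, and downstream counselling and testing with related costs. The only further content is a split into fixed and variable costs and a scenario with more patients.

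**The concern.** The two documents describe different evaluations. The protocol's payer funds a registry that finds and contacts women; the SAP's implementer is a clinic whose patients are already at hand. One of the two perspectives promised in Aim 4 has no specified analysis, one a priori outcome (ascertainment cost per patient) has disappeared, and the SAP does not say why. A registry funder deciding whether to run the programme is the reader whom the protocol names, and would find neither the programme's cost to a registry nor a payer ICER.

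**Working it through.** There is no stated figure to reproduce, so the check compares the texts, tests algebraically where the omitted costs matter, and asks whether their size can be known.

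**1. Plan against SAP**

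| Element | Protocol 6.1.A | SAP item 5 |
|---|---|---|
| Perspective | Payer and societal | Societal only |
| Implementer | Registry funder | Clinical practice |
| Recruitment and ascertainment | To be estimated; ascertainment is an a priori outcome | Excluded |
| Intervention development | To be estimated, beside a stated focus on replication | Excluded |
| Delivery and downstream | Included | Included |
| Reason for change | n/a | None given |

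**2. Do the omitted costs change the trial's ICERs?** The protocol's formula is (C_A − C_B)/(E_A − E_B). Let R be the ascertainment and recruitment cost per randomized woman, and d the cost arising after randomization. Sections 1.3.A and 1.8.A put case-finding, mailing, calls and consent before the baseline interview, with allocation at its end. R is therefore common to all arms in expectation:

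(R + d_A − R − d_B)/(E_A − E_B) = (d_A − d_B)/(E_A − E_B)

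R drops out of TCN vs UC, TP vs UC and TCN vs TP alike. A within-trial payer ICER can thus be built largely from costs the SAP already lists, by removing participant time and any patient-borne part of the downstream costs. What cannot be recovered is the payer's total outlay and the ascertainment outcome itself.

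**3. When is R incremental?** Only when the alternative is no outreach, with cost excluding R and uptake E_0. The added cost per extra CGRA is then R/(E_A − E_0). The trial does not observe E_0: its UC women were contacted and surveyed, and protocol section 1.6.A says that arm also captures priming from the surveys.

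**4. Can R be sized?** Protocol section 1.5 supports more than one yield in New Jersey:
- Headline: 7,000/700 = 10 contacts per consent.
- Component rates, 25% consent: 7,000 × 0.50 × 0.25 = 875 consents, or 8.0 contacts each.
- Component rates, 28% consent: 7,000 × 0.50 × 0.28 = 980 consents, or 7.1 contacts each.
- 875 × 0.80 = 700, so the headline 700 matches women retained rather than women consenting.

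No unit cost appears anywhere. Purely as illustration, take an **assumed** $5 to $50 per contact, and let the planned uptake differences stand in for E_A − E_0: 27 points (34% − 7%) or the 12-point minimum difference of interest (section 6.1.B).

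| Contacts per consent | R per consent | R/0.27 | R/0.12 |
|---|---|---|---|
| 7.1 | $36–357 | $132–1,323 | $298–2,976 |
| 8.0 | $40–400 | $148–1,481 | $333–3,333 |
| 10 | $50–500 | $185–1,852 | $417–4,167 |

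The range runs from trivial to substantial, and its width comes mostly from the assumed unit cost. It also treats research recruitment, with its consent and HIPAA paperwork, as if it were programme ascertainment.

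**The case against.** - **The protocol itself focuses on replication costs.** Sections 1.8.B and 6.1.A both say so. This stands for development costs: leaving them out fits that focus and should not be counted as a fault. It does not cover ascertainment, because a registry repeating the programme must find and contact women again, and section 6.1.A names recruitment and ascertainment explicitly.
- **Recruitment costs are common to all arms.** This stands in full for contrasts between arms. A reader might infer that excluding them makes the cost per additional CGRA against usual care look too low. The documents do not support that for the randomized comparison, for the reason in step 2. It could be said only of a no-outreach comparator, and pairing that comparator's costs with the trial's UC uptake would mix two controls.
- **A payer analysis may exist elsewhere.** The SAP consists of methods extracts under publication citations, and item 5 is short; it does not set out an ICER or acceptability curve either. A reader might infer that the payer question was never addressed. The documents show only that the supplied SAP specifies no such analysis.
- **The data may be lacking.** The tracking database records patient contacts in New Jersey. The time recording described in section 1.8.B is by health education specialists, and that section's cost list has no ascertainment item. Nothing says that registry staff time was logged, and contact logging at the New Mexico and Colorado registries is not described. This stands, and it limits any retrospective costing to contact counts with assumed unit costs.

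**Conclusion.** The concern holds as a gap between plan and SAP: the payer perspective and the a priori ascertainment cost are dropped, and the setting moves from registry funder to clinic, with no explanation. The societal analysis is also narrower than planned, since the protocol includes the payer costs in it.

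The gap is one of scope. It gives no ground for calling the within-trial ICERs biased, and that conclusion rests only on recruitment preceding allocation, which the protocol states. No dollar magnitude can be asserted. The illustrative figures depend on an assumed unit cost, on a yield of 7 to 10 contacts per consent, and on treating the trial's planned differences as if they were measured against no outreach. This is secondary objective 3; the primary outcome and its inference are untouched.

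**What to change.** In SAP item 5:
1. Add a payer-perspective ICER for each pair of arms, using delivery and downstream costs without participant time, and state which downstream costs the payer bears.
2. Report average ascertainment and recruitment cost per participant, from contact counts in the tracking database multiplied by a stated unit cost, with a sensitivity range.
3. Add a labelled scenario comparing the programme with no registry outreach, the only comparison in which ascertainment cost is incremental. State that the trial's UC arm was itself contacted and surveyed, so uptake without outreach is an assumption.
4. Keep the present analysis as the clinic-delivery scenario, and state why the setting moved from registry to clinic.

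The cost is modest extra analysis and no new participant data. The drawbacks are assumed unit costs wherever registry staff time was not logged, and a less favourable figure in the no-outreach scenario. Label: cheap improvement.
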